The potential use of ferumoxytol as an MRI contrast agent was evaluated in open-label feasibility studies, including one Phase I study (Protocol Number 7228-01) in healthy volunteers and two Phase II studies (Protocol Numbers 58,254-2 and 58,254-5) in subjects undergoing a diagnostic imaging procedure. In the combined studies, 70 imaging subjects were exposed to a single administration of ≤4 mg Fe/kg ferumoxytol. Results from these studies demonstrated that ferumoxytol was useful in visualizing the arterial circulation. Ferumoxytol has a long blood half-life, unlike the majority of other MRI contrast agents, enabling arterial and venous imaging for a period of several hours following injection.

March of 2015 FDA Black Box Warning: In March of 2015 the FDA placed a black box warning on ferumoxytol stating:

WARNING: RISK FOR SERIOUS HYPERSENSITIVITY/ANAPHYLAXIS REACTIONS

Fatal and serious hypersensitivity reactions including anaphylaxis have occurred in patients receiving Feraheme. Initial symptoms may include hypotension, syncope, unresponsiveness, cardiac/cardiorespiratory arrest.

- Only administer Feraheme when personnel and therapies are immediately available for the treatment of anaphylaxis and other hypersensitivity reactions.
- Observe for signs or symptoms of hypersensitivity reactions during and for at least 30 minutes following Feraheme infusion including monitoring of blood pressure and pulse during and after Feraheme administration.
- Hypersensitivity reactions have occurred in patients in whom a previous Feraheme dose was tolerated.

In the black box warning the FDA updated their recommendations of how ferumoxytol should be given. The option to give ferumoxytol (510mg) as a fast undiluted injection in approximately 1 minute has been removed. It was recommended that ferumoxytol (510mg) be given over at least 15 minutes. To accommodate for this, the dose of ferumoxytol will be given in three separate, fractionated doses. The rate of administration of the second and third doses will be slowed down to no faster than 1 mL/s.

Post-Marketing Safety

AMAG’s pharmacovigilance system proactively reviews spontaneous reports. Routine surveillance of events is performed daily and monthly signal detection and evaluation processes monitor and update the safety profile. To date the information received from the post-marketing setting is consistent with the known safety profile of ferumoxytol.

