Based on communication with AMAG Pharmaceuticals, manufacturer of ferumoxytol, all recommendations apply to iron replacement therapy where infusion rate and dilution do not impact efficacy. However, for an imaging indication certain infusion parameters are required to gain information, such as dynamic imaging. Increased infusion rate will only affect the first injection of 1 mg/kg, which is a small fraction of the full therapeutic dose, and therefore may minimally increase the risk of adverse reactions. The next two injections are given at a slower rate. The recommended 15 minutes has no scientific basis, it has been chosen arbitrarily. For MR imaging stopping the scanner for 15 minutes would be disadvantageous. Applying multiple injections, which is not the case with iron replacement therapy, may increase safety, compared to continuous injection. This may contribute to the fact that in our patient population only minor adverse reactions have been reported.

OHSU Toxicity Data

As of December 31st, 2015, a total of 671 infusions of ferumoxytol had been completed on 331 study subjects as part of OHSU's Blood Brain Barrier sponsored IRB approved protocols. The dose has ranged from 75 to 510 mg of ferumoxytol (0.5 to 11 mg/kg). In all these cases, ferumoxytol was given during MRI, using multiple IV bolus injections (1:1 diluted ferumoxytol, 3ml/s flow rate, with 20ml saline flush at the same flow rate.) In most studies the first 1mg/kg (or 75mg) was used for dynamic perfusion imaging; the remaining dose was injected in one or two subsequent bolus injections. The full 510mg was never given as a single injection. Within 42 days after ferumoxytol administration, there were 85 adverse events possibly, probably or definitely related to ferumoxytol. Among the 85 events, 43 patients had 1 event, 12 had 2 events, 3 had three events, one had 4 events and one had five events. 80% of the toxicity events occurred within 48 hours post ferumoxytol administration. There were no severe, grade 4 or 5 toxicities (CTCAE version 3 and 4) that were attributed to ferumoxytol. Table 2 shows the toxicities up to and beyond 48 hours. (Data has been published in AJNR in July of 2017).

Toxicity Category Attribute	Overall (<42 days)		Within 48 hours		>48 hours	
	# of events	Freq of events	# of events	Freq of events	# of events	Freq of events
Gastrointestinal	31	4.62%	23	3.43%	8	1.19%
Cardiac General	17	2.53%	17	2.53%	0	0.00%
Pain	17	2.53%	17	2.53%	0	0.00%

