4.5 Ferumoxytol Administration: Route and Dosing

Ferumoxytol will be injected intravenously in divided doses followed by a saline flush. The maximum total dose during the day 2 MRI will be 510mg Fe. Ferumoxytol will be diluted in normal saline (1:1 or 15mg/ml) to reduce T2* effects in the MR angiography. [126] The drug will be stored at room temperature (68-77° F) away from direct sunlight. The solution will be prepared and dispensed by the investigational drug pharmacist. It will be administered in an OHSU MR suite.

For acquisition of DSC-MRI data, ferumoxytol (5 ml=75 mg) will be injected at up to 3 ml/sec followed by a saline flush. This rate is required for adequate signal change during the dynamic imaging. When no DSC-MRI data is obtained (spine and Group 3, the rate of the first dose (5 ml=75mg) will be 1 ml/sec. The remainder of the dose will be given in a second (10 ml=150 mg) and third (19 ml=285 mg) injection at a lower flow rate, not faster than 1 ml/s. There will be a short break in time between the three injections to allow for assessment per sections 4.7.5 and 5.1. *The dilution and injection parameters of the ferumoxytol may be adjusted to obtain optimal signal changes on MRI/MRA and to decrease the possibility of an allergic reaction. Injection rate can be varied based on the participant's IV site, but the total dose will never exceed 510mg.*

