4.7.5 Data Collection

All subjects will be registered and sign a consent form which includes HIPAA authorization prior to receiving ferumoxytol.

Data, such as patient demographic information, survival times may be also collected.

In addition to the imaging data the following data collection will occur when the ferumoxytol is administered:

- Blood pressure and heart rate will be recorded on day 2 of each study visit
 - Before the first ferumoxytol infusion
 - within 10 minutes after each ferumoxytol injection
 - 30 (\pm 5) minutes after the final ferumoxytol infusion.
- Monitoring for side effects including allergic reactions will be done during the day 2 ferumoxytol MRI session.
 - After the final ferumoxytol infusion, the subject will be monitored for adverse events for 30(\pm 5) minutes and discharged if stable.
- Height, weight and lab values of the subjects will also be recorded.

Adverse events related to or potentially related to the administration of ferumoxytol will be recorded; adverse events related to the MRI's experience itself, such as claustrophobia/anxiety, nausea with GBCA injection, or discomfort due to positioning, is not being studied and will not be reported. The adverse events that will be monitored for during the infusion include localized discomfort at the IV injection site, pain, respiratory difficulties, flushing, dizziness, pruritis/rash, and any other symptoms that could be secondary to an anaphylactoid type reaction.

All data points will be flexible as subject safety while in the magnet is first priority. In addition to monitoring the above-mentioned safety parameters, an emergency code cart is located in the MR suite and can be utilized by the MR team, as well as accessed by the code team at the institution should an emergent situation arise.

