9. PWI T ₂ [*] -w axial; GEPI (TE25/TR1500/FA30) x 100 volumes 220mm x 220mm FOV 128 x 128 matrix, 3 mm contiguous, interleaved Gadoteridol bolus injection 0.1mmol/kg, 3ml/s flow rate.	2
10. T1-w sagittal FFE (TR300NEX 4) 180mm x 240mm FOV, 192 x 256 matrix, 3 mm contiguous, interleaved	3
11. SWI (TE20/TR26/FA15) 198mm x 210mm x 127 mm FOV 248 x 300 x 116 matrix	4
12. T2-w axial TSE (TE72/TR9000) 180mm x 240mm FOV, 192 x 256 matrix, 3 mm contiguous, interleaved	2
13. T1-w axial SE (TE14/TR700 NEX 4) 180mm x 240mm FOV, 192 x 256 matrix, 3 mm contiguous, interleaved	4
14. T1-w MPRAGE sagittal 3D TFE (TE3.8/TR8.2/FA8) 230mm x 230mm FOV, 230 x 230 matrix, 1 mm contiguous, interleaved	6

5.1.1.2 Day 2

Scan type	Scan Time (min)
0. Setup/localizer/B0 shimming/B1 mapping	2
1. T1-w sagittal FFE (TR300NEX 4) 180mm x 240mm FOV, 192 x 256 matrix, 3 mm contiguous, interleaved	3
2. FLAIR coronal SE/IR (TE109/TR9140/TI2500) 180mm x 240mm FOV, 192 x 256 matrix, 5mm slice thickness, 0.5mm sp	3
3. T1-w axial SE (TE14/TR700 NEX 4) 180mm x 240mm FOV, 192 x 256 matrix, 3 mm contiguous, interleaved	4
4. T2-w axial TSE (TE72/TR9000) 180mm x 240mm FOV, 192 x 256 matrix, 3 mm contiguous, interleaved	2
5. T1-w MPRAGE sagittal 3D TFE (TE3.8/TR8.2/FA8) 230mm x 230mm FOV, 230 x 230 matrix, 1 mm contiguous, interleaved	6
6. Diffusion weighted MRI axial (TE90/TR6000 SE EPI b=0, 500, 1000 s/mm ²) 220mm x 220mm FOV, 128 x 128 matrix, 3 mm contiguous, interleaved	4
7. MRA 3D-TOF (TE3.2/TR18/FA20) 170mm x 200mm x 150 mm FOV 200 x 400 x 140 matrix	5
8. SWI (TE20/TR26/FA15) 198mm x 210mm x 127 mm FOV 248 x 300 x 116 matrix	4
9. PWI T2*-w axial; GEPI (TE25/TR1500/FA30) x 100 volumes 220mm x 220mm FOV 128 x 128 matrix, 3 mm contiguous, interleaved ferumoxytol bolus injection 75mg (5ml) 2 fold diluted, up to 3ml/s flow rate. *	2
8. SWI (TE20/TR26/FA15) 198mm x 210mm x 127 mm FOV 248 x 300 x 116 matrix	4
9. PWI T2*-w axial; GEPI (TE25/TR1500/FA30) x 100 volumes 220mm x 220mm FOV 128 x 128 matrix, 3 mm contiguous, interleaved ferumoxytol injection 150mg (10 ml) 2 fold diluted, at 1ml/s flow rate. *	2
8. SWI (TE20/TR26/FA15) 198mm x 210mm x 127 mm FOV 248 x 300 x 116 matrix	4
9. PWI T2*-w axial; GEPI (TE25/TR1500/FA30) x 100 volumes 220mm x 220mm FOV 128 x 128 matrix, 3 mm contiguous, interleaved ferumoxytol injection 285mg (19ml) 2 fold diluted, at 1ml/s flow rate. *	2
10. T1-w sagittal FFE (TR300NEX 4) 180mm x 240mm FOV, 192 x 256 matrix, 3 mm contiguous, interleaved	3

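### Section 4.7.5 permits discharge 25 minutes after the last ferumoxytol injection, against the 30-minute minimum in the boxed warning quoted in Section 2.6.2.2, and visit 1 schedules no pregnancy test before ferumoxytol when on-study gadolinium is skipped

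*Combined protocol and SAP*

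**What the plan says.** **Observation.** Section 4.7.5 reads: "After the final ferumoxytol infusion, the subject will be monitored for adverse events for 30" (±5) "minutes and discharged if stable". A separate item in the same list puts the same ±5 minutes on the final blood pressure and heart rate record. Section 2.6.2.2 reproduces the FDA boxed warning: "Observe for signs or symptoms of hypersensitivity reactions during and for at least 30 minutes following Feraheme infusion". The warning adds: "Hypersensitivity reactions have occurred in patients in whom a previous Feraheme dose was tolerated".

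Section 2.6.2.2 then explains why the trial departs from the label on administration. Citing the manufacturer, it says "all recommendations apply to iron replacement therapy where infusion rate and dilution do not impact efficacy", and of the 15-minute infusion it says "For MR imaging stopping the scanner for 15 minutes would be disadvantageous". Section 4.5 makes the last of three injections the largest: "third (19 ml=285 mg) injection at a lower flow rate, not faster than 1 ml/s". The brain Day 2 schedule in Section 5.1 matches: "ferumoxytol injection 285mg (19ml) 2 fold diluted, at 1ml/s flow rate".

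**Pregnancy test.** Section 4.7.1.1 places the visit-1 test before any gadolinium-based contrast agent (GBCA) given on study. The same paragraph accepts a gadolinium scan done off study, with repetition left to the investigator. It also sends subjects with GFR below 50 or a GBCA contraindication straight to Day 2, the ferumoxytol day. Section 4.7.3 requires a pregnancy test at each later visit. Section 4.2.8 excludes pregnant women because of fetal risk.

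**The concern.** A symmetric tolerance around 30 minutes cannot satisfy a rule that sets 30 minutes as the floor. The hazard behind that rule is fatal and serious hypersensitivity, and the protocol's reasons for departing from the label (rate, dilution, infusion length) do not bear on how long the subject waits afterwards. Giving the drug faster than the label advises is, if anything, a reason to keep the full observation period. Because reactions have followed previously tolerated doses, and Section 4.7.3 allows up to four study visits, an uneventful earlier visit does not justify a shorter wait.

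The pregnancy gap lies on a planned route. Primary objective 3.1.4 enrols subjects who should not receive gadolinium, and those subjects bypass the step to which the visit-1 test is attached. Staff who follow the visit schedule exactly could give ferumoxytol to a woman with an undetected pregnancy.

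**Working it through.** **1. Permitted window**
- Section 4.7.5: 30 − 5 = 25 minutes to 30 + 5 = 35 minutes.
- Minimum in Section 2.6.2.2: 30 minutes.
- Largest shortfall: 30 − 25 = 5 minutes; 5/30 = 16.7%.
- Dose in the last injection (Section 4.5): 285/510 = 55.9%.

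**2. Would imaging alone keep the subject for 30 minutes?** These are the listed Day 2 scan times in Section 5.1, assuming sequences run back to back. Brain and carotid or aorta include the run that carries the third injection. Lower extremity counts from the first-pass angiogram, because that table does not mark the injections.

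| Schedule | Sum (minutes) | Total |
|---|---|---|
| Brain | 2 + 3 + 4 + 2 + 4 + 6 | 21 |
| Spine | 4 + 4 + 4 + 3 + 3 + 4 | 22 |
| Carotid or aorta | 3 + 4 + 4 + 3 | 14 |
| Lymph node | 4 + 4 | 8 |
| Lower extremity | 0:11 + 4:35 + 4:12 + 3:50 = 12:48 | 12.8 |

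None reaches 30. The abdominal subgroup (n = 50) adds 2 + 6 × 1 = 8 minutes. If run after the main schedule, that gives 29 for brain, 30 for spine and 22 for carotid or aorta.

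**3. Observation outside the scanner**
- Brain: 19 minutes of scanning follow the perfusion run, or 21 if the injection opens that 2-minute run. Discharge at 25 minutes leaves 25 − 21 = 4 to 25 − 19 = 6 minutes. At 30 minutes it is 30 − 21 = 9 to 30 − 19 = 11.
- Spine: 25 − 22 = 3 minutes, against 30 − 22 = 8.

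Gaps between sequences would shorten these times.

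**4. Pregnancy test at visit 1, by route**

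| Route to Day 2 ferumoxytol | Scheduled test |
|---|---|
| Gadolinium given on study | Yes (4.7.1.1) |
| Off-study gadolinium scan, not repeated | None |
| Known GFR below 50 or GBCA contraindication | None |
| Any later visit | Yes (4.7.3) |

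Sections 4.3 (pre-screen), 4.4 (registration), 4.5 (dosing), 4.7.1.2 (Day 2) and 4.7.5 (data collection) name no pregnancy test. In Section 4.7.3 the gadolinium condition is attached to kidney function only, so the pregnancy test there is unconditional. The visit-1 wording therefore looks like a drafting oversight. The documents give no figure for how many women take the two untested routes.

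**The case against.** **Observation.** The target is already 30 minutes, and the footnotes to the Section 5.1 schedules give a 30-minute vital-sign check with no tolerance. On this view ±5 is a recording tolerance that was carried onto the discharge line. Discharge also requires stability, subjects are monitored during scanning, and a code cart is in the MR suite. The fastest injection gets a longer watch: on the brain schedule it starts 2 + 4 + 2 + 4 = 12 minutes before the third, so discharge at 25 minutes still follows it by 37. The warning counts time after infusion, so minutes outside the scanner are not its measure, and the shorter schedules leave more of them (carotid or aorta 25 − 14 = 11, lymph node 25 − 8 = 17). Section 2.6.2.2 reports 671 infusions at the site with no grade 4 or 5 toxicity attributed to ferumoxytol, and nothing shows reactions arising between 25 and 30 minutes.

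Much of this is fair, and it limits the size of the point. The tolerance may well be accidental, and the out-of-scanner minutes are context only. But the tolerance is written into the discharge sentence itself, and the footnotes set no minimum stay. Stability at 25 minutes is not observation to 30, and a code cart in the MR suite does not help someone who has left. No such events in 671 infusions leaves an approximate 95% upper limit of 3/671 = 0.45%, treating infusions as independent, which cannot justify dropping a precaution against a rare event.

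**Pregnancy.** The exclusion binds, and registration requires a completed eligibility checklist, which may name a test. Contraception (4.1.6) and withdrawal on pregnancy (8.3.4) are further controls. The gap covers visit 1 only, and only women who skip on-study gadolinium. All of this is true. Still, contraception does not detect an existing pregnancy, withdrawal acts only once a pregnancy is known, and no visible section schedules the test on these routes.

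**Conclusion.** Both parts hold. A subject may be discharged up to 5 minutes (17%) before the quoted minimum, with no reason given, after an injection carrying 56% of the dose. At visit 1, no pregnancy test is scheduled before ferumoxytol when gadolinium is not given on study. The first conclusion rests on the literal discharge rule. The second rests on the visible text, since the eligibility checklist is not reproduced. The scan-time figures assume no gaps between sequences. Neither point alters a sample size, estimate or analysis. They are safety-procedure gaps that should be fixed because the hazards are serious and the remedy is small.

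**What to change.** Amend two sentences.

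- **Section 4.7.5:** make 30 minutes the floor. For example: *Observation for adverse events continues for at least 30 minutes (30 to 35) after the last ferumoxytol injection; a stable subject may then leave.* The ±5 minutes can stay on the blood pressure and heart rate time point.
- **Section 4.7.1:** detach the test from gadolinium. For example: *Women of child-bearing potential have a pregnancy test before ferumoxytol at every study visit, whether or not GBCA is given on study.*

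The cost is one amendment, up to 5 more minutes of observation per visit, and one routine test, already used in the trial, for the women now missed. No arm, reader or imaging is added.

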4.8 Duration and Follow-up Care

Study duration is up to 2 years. Subjects will be followed for 4-6 weeks after each ferumoxytol administration. See section 4.7.4.

4.9 Evaluation of Organ Uptake and Clearance of Ferumoxytol

This additional part of the study will evaluate the time needed after ferumoxytol administration before the MR signal in certain organs including the liver, spleen, pancreas and bone marrow returns to a level which allows clinically satisfactory MR imaging of these organs. Various MR sequences will be tested to determine which is the most applicable to reduce confounding effect of prior ferumoxytol administration. Abdominal MR scans will be performed in 50 subjects before and at multiple time points after the first ferumoxytol administration. These subjects will be a subgroup from groups; 1, 2 and 3. The time points will be: before, shortly after, 24-48 h after, 1 week after, 1, 2, 3 and 6 months after ferumoxytol administration. Once signal changes are no longer present, subsequent imaging will not be necessary. The sequences will be short, without full anatomical coverage.

If a subject does not qualify for the abdominal imaging (because of previous iron injection) or chooses not to participate in the abdominal imaging, the subject can still be enrolled in and complete the primary group imaging sessions.

The MRI sequences are detailed in section 5.1.

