4 TRIAL DESIGN

4.1 Inclusion Criteria

4.1.1 Group specific inclusion criteria:

Group1: Subjects must have a radiological or histological diagnosis of dural or central nervous system (CNS) parenchymal based inflammatory, vascular or demyelinating lesions. This includes but is not limited to unknown lesions, meningioma, neuroma, stroke, multiple sclerosis (MS) or related diseases such as acute disseminated encephalomyelitis (ADEM). Subjects with a CNS inflammatory lesion that is suspicious for neoplasm or radiation induced inflammation (vasculitis) will also be included.

Group2: Subjects must have radiological suspected diagnosis of vascular CNS lesions such as ischemic stroke, TIA with suspected carotid embolic origin, or vasculopathy involving the carotids (including diagnosed carotid stenosis >50%), the aorta, the arteries of the extremities, or diagnosed thrombosis of the intraabdominal, pelvic or extremity veins.

Group3: subjects must have clinical or radiological diagnosis of enlarged cervical lymph nodes in which inflammatory processes (reactive lymph nodes) is part of the differentials.

Subgroup: any subject in a primary group who agrees to participate in the abdominal imaging portion of the study.

4.1.2 Subjects must be 18 years or older for inclusion in this study.

4.1.3 Subjects must have a Karnofsky of 30% or greater.

4.1.4 Subjects agree to follow up approximately 4-6 weeks after each infusion of ferumoxytol.

4.1.5 All subjects or their authorized representative must sign a written informed consent and give HIPAA authorization in accordance with institutional guidelines.

4.1.6 Sexually active women of child-bearing potential and men must agree to use adequate contraception (hormonal or barrier method of birth control; or abstinence) at the start of study treatment and for the duration of study treatment. Should a female become pregnant or suspect she is pregnant while participating in this study, she should inform her treating physician immediately.

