4.2 Exclusion criteria

4.2.1 Subjects with clinically significant signs of uncal herniation, such as acute pupillary enlargement, rapidly developing motor changes (over hours), or rapidly decreasing level of consciousness.

4.2.2 Subjects who have a contraindication for MRI: metal in their bodies (a cardiac pacemaker or other incompatible device).

- 4.2.3 Subjects with known allergic or hypersensitivity reactions to parenteral iron, parenteral dextran, parenteral iron-dextran, or parenteral iron-polysaccharide preparations (Investigator's Drug Brochure, Combidex 2002; Advanced Magnetics Inc; Investigator's Drug Brochure, Code 7228; 2003 Advanced Magnetics Inc).
- 4.2.4 Subjects with known hepatic insufficiency or cirrhosis
- 4.2.5 Subjects with known or suspected iron overload (genetic hemochromatosis or history of multiple transfusions)
- 4.2.6 Subjects with symptoms or signs of hemodynamic instability.
- 4.2.7 HIV-positive patients on combination antiretroviral therapy are ineligible because of the potential for pharmacokinetic interactions with ferumoxytol.
- 4.2.8 Pregnant or lactating women are excluded from this study because of possible risk to the fetus or infant.
- 4.2.9 Subjects with three or more drug allergies from separate drug classes.
- 4.2.10 Subgroup only exclusion criteria: prior administration of ferumoxytol.

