4.7.1.1 Day 1 (gadolinium MRI)

The subject will have an anatomical MRI (brain &/or spine [group1], carotids and/or aorta and/or other arteries or veins [group2] or cervical lymph nodes [group3]) with and without gadolinium, which may include DWI, MRA or perfusion study. This MRI will be done

within 7 days prior to the ferumoxytol infusion and may have been done off study as medically necessary; and may or may not be repeated at PI's discretion. Laboratory testing (creatinine/GFR) to check kidney function and a pregnancy test in women of child bearing potential will be done prior to GBCA administration done on study. Subjects with renal insufficiency (GFR <50ml/min/1.73m²) and/or contraindication to GBCA, will not undergo imaging with gadolinium, they will proceed to "Day 2". Short abdominal MR imaging as a baseline will be performed in the subgroup prior to any ferumoxytol administration and may be done either day 1, or on day 2 prior to ferumoxytol administration).

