5.2 Criteria for Image evaluation

Contrast-Enhanced MRI: All the superparamagnetic iron oxide agents display a much more effective MR relaxation than their paramagnetic counterparts. The following changes will be evaluated on ferumoxytol enhanced MRI when compared to non enhanced MRI images: increased or decreased signal on T1-weighted SE images, and decreased signal on T2-weighted SE images.

Image Analysis of Lesions: In order to determine the sensitivity of the gadolinium and ferumoxytol contrast agents in revealing abnormally enhancing brain regions, the gadolinium and ferumoxytol scans will be independently assessed on two measures: a) the number of intensity-enhanced abnormalities and b) the volume of enhancements.

Contrast enhancements in each scan will be identified by two radiologists who will review the gadolinium and ferumoxytol scans and identify regions of contrast enhancement using a drawing tool to identify voxels that are enhanced by the contrast agent. These measurements will yield a count of the number of lesions and the volume of each lesion detected for each scan. Differences in the number of lesions detected and the volume of each lesion will be resolved by a third neuroradiologist.

For carotid stenosis, degree of anatomical narrowing will additionally be described using standard NASCET criteria in addition to subjective and quantitative characterization of vessel wall presence or absence and thickness (where applicable), of enhancement.

The analysis of cervical lymph nodes will be performed by two radiologists, by analyzing the heterogeneity of the lymph nodes. Cellular ferumoxytol uptake results in a signal loss of the normal functioning lymphatic tissue, whereas the lack of ferumoxytol uptake will result in areas with higher signal, indicating etiologies different from reactive changes. Diagnostic accuracy will be compared between gadolinium and ferumoxytol, and confirmed with biopsy specimens in case lymph node sampling is performed.

MR analysis of abdominal organs and bone marrow with ferumoxytol uptake and clearance will be evaluated by comparing images at various time points with pre-ferumoxytol baseline scans.

Discipline reviews

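### The abdominal clearance subgroup has two inconsistent eligibility wordings on prior iron, and under the narrower one the reference scan may already be altered by another injected iron product

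*Combined protocol and SAP*

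**What the plan says.** Objective 3.2.3 is to describe the time course of iron uptake and clearance in abdominal organs and bone marrow after the first ferumoxytol injection, in 50 subjects drawn from the three primary groups.

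Two current passages say who is kept out of this subgroup:

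- Section 4.2.10: "Subgroup only exclusion criteria: prior administration of ferumoxytol".
- Section 4.9, in a sentence allowing a subject who does not qualify to remain in the main study: not qualifying is explained as "because of previous iron injection".

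Inclusion (4.1.1) is open to "any subject in a primary group who agrees to participate in the abdominal imaging portion of the study". On the baseline scan, 4.7.1.1 says: "Short abdominal MR imaging as a baseline will be performed in the subgroup prior to any ferumoxytol administration". Section 5.2 says organ uptake and clearance "will be evaluated by comparing images at various time points with pre-ferumoxytol baseline scans". Under 4.7.1.5 and 4.9, scanning of a subject ends once ferumoxytol, or the signal change, is no longer seen. Section 4.7.1.5 removes subjects from the subgroup if they receive more ferumoxytol; it does not mention other iron products.

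**The concern.** The two wordings differ in scope. A subject previously given a different injected iron product passes 4.2.10 and fails 4.9 as literally written, so staff at enrolment cannot follow both.

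The difference matters because the subject's own pre-ferumoxytol scan is the stated comparator. If earlier iron still affects that scan, later differences from it no longer reflect ferumoxytol alone. The stopping rule adds to the problem: a scan that wrongly looks clear ends that subject's series, and the later images that could have shown the error are not taken.

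The situation is plausible from the documents alone. Subjects with renal disease are enrolled by design (3.1.4), and the post-marketing background (2.6.2.2) describes intravenous iron sucrose as a comparator treatment for iron deficiency anaemia in chronic kidney disease.

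**Working it through.** The plan gives no figure to reproduce: the 50 subjects have no stated power, precision or effect size behind them, and 6.1 specifies descriptive summaries. The check is therefore a comparison of text, followed by reasoning about direction and an illustration.

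**Step 1: does any other provision close the gap?**

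| Provision | What it covers | Closes the gap? |
|---|---|---|
| 4.1.1 and 4.6, subgroup definition | Willingness to take part | No |
| 4.2.3 | "Subjects with known allergic or hypersensitivity reactions to parenteral iron" and related products: reactions, not exposure | No |
| 4.2.5 | Iron overload, with hemochromatosis and multiple transfusions as the named causes | No |
| 2.6.2.1 | States that overload need not be screened for when there is no history of it | No |
| 4.7.1.1 | Baseline scan must precede ferumoxytol only | No |
| 4.7.5 | Data collected; prior or concurrent iron products are not named | No |

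Nothing resolves the difference, and affected subjects may not be identifiable at analysis.

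**Step 2: which way could the comparison err?** Assume, for illustration, that iron effects on signal add up. Let *f(t)* be the size of the ferumoxytol effect at time *t* and *b(t)* that of other iron, with *t* = 0 at the baseline scan. The change from baseline is then

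*f(t)* + *b(t)* − *b(0)*.

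- If *b(t)* = *b(0)*, so the earlier iron is stable, the change equals *f(t)*. The subject's own baseline removes the earlier iron and there is no bias.
- If *b(t)* < *b(0)*, so the earlier iron is clearing, the change reaches zero while *f(t)* = *b(0)* − *b(t)* is still above zero. Clearance appears too early and scanning may stop too soon.
- If *b(t)* > *b(0)*, because other iron is given during follow-up, the change stays above zero after *f(t)* has reached zero. Clearance appears too late.

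If the baseline signal is already close to the limit of what iron can do, additivity fails and ferumoxytol uptake itself could be understated. The documents do not say which of these cases would apply.

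**Step 3: how many subjects?** The documents give no share *p* with earlier non-ferumoxytol injected iron. Each affected subject is 1/50 = 2% of the subgroup. Treating subjects as independent, the expected number is 50*p* and the chance of at least one is 1 − (1 − *p*)^50:

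| Assumed *p* | Expected number of 50 | Chance of at least one |
|---|---|---|
| 1% | 0.5 | 39.5% |
| 2% | 1.0 | 63.6% |
| 5% | 2.5 | 92.3% |
| 10% | 5.0 | 99.5% |
| 20% | 10.0 | about 100% |

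Every value of *p* is an assumption. The inconsistency exists whatever *p* is.

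**The case against.** The best defence is that 4.9 does not set a second rule. Its phrase is a parenthesis in a permissive sentence, the only formal subgroup exclusion is 4.2.10, and the surrounding text of 4.9 is about ferumoxytol throughout. The phrase may simply be shorthand for a previous ferumoxytol injection. That reading is natural and cannot be ruled out. But the text does not say so, and if it is what was meant, 4.9 still needs correcting.

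Second, 4.9 states the aim as the time until organ signal is good enough for clinical imaging, so return to baseline is not the whole definition. This stands. However, comparison with baseline is the only evaluation method that 5.2 describes for these organs, and the disappearance of signal change ends the scanning.

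Third, a reader might infer that such subjects' baselines certainly contain residual iron, that their clearance results are meaningless, or that a sizeable fraction of the subgroup is affected. The documents support none of these. They give no retention time or MR effect for any other iron product. Stable earlier iron would largely cancel in the comparison with the subject's own baseline. No count of renal subjects is given, and Group 1, enrolled for CNS lesions, may supply up to 260 of 295 subjects (260 + 25 + 10 = 295; 260/295 = 88%). Much of the background on injected iron in kidney disease also concerns ferumoxytol itself, which 4.2.10 already excludes. Nor is the problem beyond repair: if exposure is recorded, affected subjects can be identified and handled separately, although scans not taken cannot be recovered.

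**Conclusion.** The inconsistency between 4.2.10 and 4.9 is real, and nothing else in the documents resolves it. Under 4.2.10 a subject can enter the subgroup with a reference scan that may already be altered by other injected iron. This could bias the apparent return to baseline and end scanning at the wrong time.

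Bias is a possibility, not a demonstrated effect. It requires that such subjects are enrolled, that their earlier iron still affects abdominal signal at baseline, and that this effect changes during follow-up or is close to saturation. The documents establish none of these, so the size is unknown; the shares of 1% to 20% used above are illustrations only.

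The consequence is confined to secondary objective 3.2.3, which is descriptive and belongs to a study that calls itself exploratory. The primary comparisons with gadolinium are not touched. It is worth correcting because the correction is small and the exposure information may otherwise not be collected.

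**What to change.** 1. Reconcile 4.2.10 and 4.9 into one rule. The preferable form aligns 4.2.10 with the broader wording of 4.9, so that prior ferumoxytol or other injected iron excludes a subject from the abdominal subgroup only. If the sponsor meant ferumoxytol alone, 4.9 should say so.
2. Record prior injected iron (product and date) at enrolment. This is needed under either rule, so that affected subjects can be identified.
3. For consistency, record other injected iron given during the 6-month follow-up, and flag or leave out later abdominal scans from those subjects in the descriptive clearance summary. Section 4.7.1.5 does not contradict another passage here; the step gives follow-up the same protection as the baseline.

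The cost is one amended eligibility sentence, one question at enrolment and one item during follow-up. A few subjects, probably renal, would be lost from the subgroup. They stay in their primary groups, as 4.9 already provides, but the clearance results would then describe fewer renal subjects, and this should be stated when they are reported.
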